Version 2.0 (Dated 24 August 2016) of this Protocol is the first amendment to this clinical trial and contains the following modifications:

- All subjects are now required to start prophylaxis treatment with pneumocystis jiroveci pneumonia (PCP) and antiviral therapy, whereas this was previously at investigator discretion (See Section 6.2.2);
- The phrasing of response assessment intervals has been revised for clarity from “at Weeks 12, 24, 36, 48, and every 12 weeks thereafter,” to “following the completions of cycles 3, 6, 9, 12, 15, 18 and every 3 cycles thereafter”;
- Schedule of assessments and treatment schedule (Section 5) was updated, including
  - Revised wording for Tumor Evaluation (as listed above) and
  - Updated Urine Pregnancy Test schedule,
- The shelf life of ublituximab has been increased to 36 months from 24 months when stored between +2°C / +8°C to reflect newly available stability data on ublituximab drug product; and
- Sections 7.1.1, and 7.2.1 were updated to include the most recent adverse event information related to ublituximab and TGR-1202 corresponding to the latest Investigator Brochures.

Version 3.0 (Dated 7 March 2017) of this Protocol is the second amendment to this clinical trial and contains the following modifications:

- Inclusion criteria #1a has been updated to provide a minimum time on a study arm of 2 cycles
- Inclusion criteria #2 has been updated to include units (per microliter) in regard to absolute neutrophil count and platelet count;
- Exclusion criteria #4 has been updated to clarify prophylaxis as “anti-pneumocystis pneumonia prophylaxis”;
- Exclusion criteria #6 has been added to exclude subjects with prior live virus vaccines;
- Appendix B – Contraceptive Guidelines and Pregnancy has been revised to delete the word “highly” effective as well as to include follow up recommendations for subjects entering the study from treatment arm B in study UTX-TGR-304 (obinutuzumab arm).
- CT scan evaluation has been revised to allow for every 3 or 6 cycle CT Scans after Cycle 9 at the discretion of the investigator, to limit exposure to radiation.
- The 21-day timeframe for signing informed consent has been removed.

Version 4.0 (Dated 29 March 2017) of this Protocol is the third amendment to this clinical trial and contains the following modifications:

- Definition of Serious Adverse Event has been updated.

Version 5.0 (Dated 20 October 2017) of this Protocol is the fourth amendment to this clinical trial and contains the following modifications:

- Inclusion Criteria 1a was updated to include the statement: There is no required timeframe to begin treatment on the 204 protocol, however, if other therapies to treat the disease are implemented in the interim, the subject will not be eligible to enroll in the study.
- Exclusion Criteria 4 was updated to clarify the use of anti-pneumocystis pneumonia prophylaxis

- Treatment schedule in section 5 was updated to:
  - increase the screening period from 21 to 28 days.
  - include MRD testing for subjects who have a PR
  - increase the window for scans from +/- 7 days to +/- 14 days
- Section 6.1 was updated to specify the treatment schema for subjects crossing over from each of the 4 arms in the 304 protocol
- Section 6.2.1.3.1 and Section 7.1 were both updated to include information regarding a new vial size for ublituximab;
- Sections in 6.4 were updated with the latest dose delay/modification guidance for ublituximab and TGR-1202. This section also includes guidance for diarrhea and colitis events.
- Section 6.4.3 was updated to include process of transferring drug from the 304 protocol, if applicable
- Sections 7.1.1, and 7.2.1 were updated to include the most recent adverse event information related to ublituximab and TGR-1202 corresponding to the latest Investigator Brochures;
- The following statement was removed from section 8.2.1: “At follow-up time points, the LDs for individual lesions and the SPD of all nodal target lesions will be considered. Because nodal target lesions that have one or both diameters  $>0$  cm and  $< 1.0$  cm cannot be reliably measured, a default value of 1.0 cm will be assigned for each diameter that meets these criteria and the resulting PPD will be used in SPD calculations. Based on this convention, a CR may be achieved even if an SPD value is  $>0$  cm^2 (i.e., if all lymph nodes measure  $< 1.0$  cm^2)” to allow for more accurate measurements of nodal target lesions.
- Minor administrative updates and typographical errors were corrected throughout.
- Updated throughout to include the generic name of TGR-1202: umbralisib

Version 6.0 (Dated 22 January 2019) of this Protocol is the fifth amendment to this clinical trial and contains the following modifications:

- Protocol updated throughout with minor editorial and administrative changes.
- [Section 3](#) Eligibility Criteria updated as follows:
  - Inclusion Criteria 2a clarified to account for subjects with cytopenias due to bone marrow involvement.
  - Inclusion Criteria 2b clarified to allow subjects with Gilbert’s Disease and Autoimmune Hemolytic Anemia.
  - Inclusion Criteria 2d updated to utilize the modified Cockcroft Gault utilizing ideal body mass.
  - Exclusion Criteria 4 added as follows - Evidence of chronic active Hepatitis B (HBV, not including subjects with prior hepatitis B vaccination; or positive serum Hepatitis B antibody) or chronic active Hepatitis C infection (HCV), cytomegalovirus (CMV), or known history of HIV. If HBc antibody, HCV antibody or CMV IgM is positive the subject must be evaluated for the presence of HBV, HCV, or CMV by PCR
- [Section 5](#) Study Assessments and Treatment Schedule updated as follows:
  - Tumor Evaluations updated within the table with the following language - Evaluations are to be obtained during cycles 3, 6 & 12. Following cycle 12, evaluations should occur at least every 12 cycles.

- Serum Virology added to include HBsAG, HBc antibody, HCV antibody, and CMV IgG and IgM at screening and CMV surveillance added while subjects are receiving umbralisib.
- [Section 5 - Table 2](#): Follow Up Assessments Schedule added to clarify follow up assessments if a subject comes off study drug.
- [Section 6](#) Treatment Plan: Updated to clarify PJP and anti-viral prophylaxis language and modified to provide more clear guidelines for timing of pre-medications for ublituximab.
- [Section 6.4](#) Dosing Delays/Dose Modification: Removed requirement for subjects to discontinue study drugs if held for more than 28 days.
- [Section 7.3](#) Comprehensive Adverse Events and Potential Risks (CAEPRS) – Ublituximab + TGR-1202 Combination updated based on Investigator Brochures Version 6.0, dated 20JUL2018.

## STUDY SYNOPSIS

Protocol No.	UTX-TGR-204
Study Title	A Multi-Center, Open-Label, Compassionate Use Extension Study of Ublituximab (TG-1101) in Combination with Umbralisib (TGR-1202) for Patients Previously Enrolled in Protocol UTX-TGR-304
Sponsor	TG Therapeutics Inc. (New York, NY, USA)
Study Sites & Enrollment	This study will be opened only at sites that participate in the parent trial UTX-TGR-304 .
Study Rationale	
Ublituximab (also known as TG-1101) is a glycoengineered monoclonal antibody that binds to the trans-membrane antigen CD20 found on B-lymphocytes. The binding of ublituximab induces an immune response that causes lysis of B cells.
 
Umbralisib (also known as TGR-1202) is a highly specific and orally available phosphoinositide-3-kinase (PI3K) delta (<math>\delta</math>) inhibitor with nanomolar inhibitory potency, and high selectivity over the alpha, beta, and gamma Class I isoforms of PI3K. The delta isoform of PI3K is highly expressed in cells of hematopoietic origin, and strongly upregulated, and often mutated in various hematologic malignancies.
 
Ongoing studies are evaluating the combination of ublituximab + TGR-1202 in subjects who previously relapsed from or are refractory to anti-CD20 antibody therapy as well as PI3K delta inhibitor therapy (Lunning, et. al. ASCO 2015, Fowler, et. al. ASCO 2015). A Phase 3, randomized study (UTX-TGR-304) to assess efficacy and safety of ublituximab in combination with TGR-1202 compared to obinutuzumab in combination with chlorambucil in subjects with CLL is being conducted. UTX-TGR-304 will also compare ublituximab alone and TGR-1202 alone to the combination of ublituximab plus TGR-1202. This protocol is intended to provide the opportunity for subjects who progress on UTX-TGR-304 Treatment Arms B (obinutuzumab plus chlorambucil), C (ublituximab), or D (TGR-1202) to receive treatment with the combination. Additionally, at the time of UTX-TGR-304 study closure, this protocol is intended to allow subjects from Treatment Arm A (ublituximab plus TGR-1202) to continue combination therapy.

Study Objectives	
For subjects previously on Arms B, C, & D of Study UTX-TGR-304:
 
Primary Objectives
 
 
To observe the overall response rate (ORR) defined as the sum of complete responses (CR) and partial responses (PR)
 
 
Secondary Objective
 
 
To observe the progression-free survival (PFS) and duration of response (DOR)
 
To observe the % of subjects that achieve MRD negativity
 

	
 
To observe the safety of ublituximab in combination with TGR-1202
 
 
For subjects previously on Arm A of Study UTX-TGR-304:
 
Primary Objectives
 
 
To evaluate the progression-free survival (PFS) and duration of response (DOR)
 
 
Secondary Objective
 
 
To evaluate the safety of ublituximab in combination with TGR-1202
 

Inclusion Criteria	
 
Prior treatment in clinical trial UTX-TGR-304       
 
Confirmed progression by IRC from Arms B, C, or D after at least two cycles of treatment in trial UTX-TGR-304. There is no required timeframe to begin treatment on the UTX-TGR-204 protocol; however, if other therapies to treat the disease are implemented in the interim, the subject will not be eligible to enroll in the study.
 
Non-progressing subjects from Arm A may be eligible for enrollment when protocol UTX-TGR-304 is completed
 
 
 
Adequate organ system function, defined as follows:       
 
Absolute neutrophil count (ANC) <math>> 750 \times 10^3/\text{mm}^3</math> (0.75 K/<math>\mu\text{L}</math>) mL of blood / platelet count <math>> 40 \times 10^3/\text{mm}^3</math> (40 K/<math>\mu\text{L}</math>) mL of blood unless cytopenias are related to bone marrow involvement.
 
Total bilirubin <math>\leq 1.5</math> times the upper limit of normal (ULN) with the exception of Gilbert's Disease and Autoimmune Hemolytic Anemia.
 
Alanine aminotransferase (ALT) and aspartate aminotransferase (AST) <math>\leq 2.5 \times \text{ULN}</math> if no liver involvement or <math>\leq 5 \times \text{ULN}</math> if known liver involvement
 
Calculated creatinine clearance <math>> 30</math> mL/min (as calculated by the Modified Cockcroft-Gault formula (using ideal body mass [IBM])).
 
 
 
ECOG performance status <math>\leq 2</math>
 
Ability to swallow and retain oral medication
 
Willingness and ability to comply with trial and follow-up procedures, give written informed consent
 

Exclusion Criteria	
 
Prior treatment with obinutuzumab + chlorambucil (Arm B subjects) or ublituximab (Arm C subjects) within 7 days of Cycle 1/Day 1.
 
Subjects refractory to (progressing on) UTX-TGR-304 Treatment Arm A (ublituximab + TGR-1202).
 
Known histological transformation from CLL to an aggressive lymphoma (i.e. Richter's transformation).
 
Evidence of chronic active Hepatitis B defined as Hepatitis B surface antigen positive or Hepatitis B DNA positive by PCR (HBV, NOT including subjects with prior hepatitis B vaccination who are Hepatitis B surface antibody positive only;) or chronic active Hepatitis C infection (HCV) defined as Hepatitis C RNA positive by PCR, cytomegalovirus (CMV) DNA positive by PCR, or known history of HIV. If HBc antibody, HCV antibody or CMV IgG and/or IgM antibody is positive the subject must be evaluated for the presence of HBV, HCV, or CMV by PCR - See Appendix D.
 

	
 
5. Evidence of ongoing systemic bacterial, fungal or viral infection, except localized fungal infections of skin or nails. NOTE: Subjects may be receiving prophylactic antiviral or antibacterial therapies at investigator discretion. Use of anti-pneumocystis pneumonia prophylaxis is required prior to Cycle 1/Day 1 and for the first 2 cycles. After cycle 2, is per investigator discretion.
 
6. Woman who are pregnant or lactating.
 
7. Live virus vaccines four (4) weeks prior to or during ublituximab therapy.
 

Efficacy Endpoints	
Overall response rate (ORR) ORR is defined as sum of CR and PR rates.
 
Complete Response (CR) Rate CR rate is defined as the proportion of subjects who achieve a CR.
 
Progression-free survival (PFS) PFS is defined as the interval from enrollment to the earlier of the first documentation of definitive disease progression or death from any cause. Definitive disease progression based on standard criteria (Hallek et al. 2008) and occurring for any reason (i.e., increasing lymphadenopathy, organomegaly or bone marrow involvement; decreasing platelet count, hemoglobin, or neutrophil count; or worsening of disease-related symptoms) other than lymphocytosis.
 
Minimal Residual Disease (MRD) Negativity Rate MRD negativity rate is defined as the proportion of subjects who are MRD negative.
 
Duration of response (DOR) DOR is defined as the interval from the first documentation of CR or PR to the earlier of the first documentation of definitive disease progression or death from any cause.

Safety Endpoints	All AEs will be reported and evaluated using National Cancer Institute's Common Terminology Criteria (CTCAE) v4.0.
Study Design	
This study is intended to serve as a compassionate use study to allow subjects who have previously progressed on Arms B, C & D in the parent trial UTX-TGR-304 to receive ublituximab plus TGR-1202. Those subjects must have had confirmed disease progression by the independent radiology committee (IRC). Additionally, at the termination of study UTX-TGR-304, non-progressed subjects from Treatment Arm A may be enrolled to this study.
 
Subjects from Treatment Arms B, C, and D may start treatment with ublituximab + TGR-1202, while subjects entering this study from Treatment Arm A may continue their treatment until they show disease progression, are unable to continue treatment for any reason such as lack of tolerability, or until the treatment is commercially available.

	
During the study period, all subjects will be evaluated for response by CT and/or MRI. Evaluations are to be obtained at approximately cycles 3, 6, and 12. Following cycle 12, evaluations should occur at least every 12 cycles unless clinically indicated sooner. Subjects followed for PFS off treatment should have scans completed per institutions standard of care and reported in the EDC until progressive disease or subject begins another anti-cancer treatment. Date of progression, beginning of new treatment, and/or death should be entered in the eCRF. Subjects should remain on study treatment until the occurrence of definitive disease progression, unacceptable toxicity, or withdrawal from the study due to investigator discretion or other reasons. Subjects who discontinue from study treatment and have not progressed should continue to be followed for progression.
																								

Dosing Regimen
	
Each Cycle = 28 days
 
Ublituximab + TGR-1202 Regimen
 
Subjects will receive ublituximab + TGR-1202 as described in protocol UTX-TGR-304. Subjects will receive TGR-1202 orally daily and ublituximab as an intravenous administration as per the schedule specified in the parent protocol and outlined in the table below. This schedule is specific to subjects that were in UTX-TGR-304 Arms B, C, and D. Subjects previously in Arm A of protocol UTX-TGR-304 will continue the schedule received while on study UTX-TGR-304 with TGR-1202 orally daily, and ublituximab every 3 months.
 
Cycle 1:
 
  
 Ublituximab	TGR-1202	
 
 Day 1	Day 2	Day 8 & 15	Daily	
   
 150 mg	750 mg	900 mg	800 mg	
  
 
Cycles 2 through 6:
 
  
 Ublituximab	TGR-1202	
   
 Day 1	Daily	
 
 900 mg	800 mg	
  
 
After Cycle 6:
 
  
 Ublituximab	TGR-1202	
   
 Day 1, Q3 months	Daily	
 
 900 mg	800 mg	
  
 
Ublituximab Premedication:
 
Ublituximab should be started approximately 30 minutes after the conclusion of the last pre-medication infusion and should include an antihistamine (diphenhydramine 50 mg or equivalent), and a corticosteroid (dexamethasone 10-20 mg or equivalent). If pre-medication is given orally, they should be given approximately 45-60
	Ublituximab			TGR-1202	Day 1	Day 2	Day 8 & 15	Daily	150 mg	750 mg	900 mg	800 mg	Ublituximab	TGR-1202	Day 1	Daily	900 mg	800 mg	Ublituximab	TGR-1202	Day 1, Q3 months	Daily	900 mg	800 mg
Ublituximab			TGR-1202																						
Day 1	Day 2	Day 8 & 15	Daily																						
150 mg	750 mg	900 mg	800 mg																						
Ublituximab	TGR-1202																								
Day 1	Daily																								
900 mg	800 mg																								
Ublituximab	TGR-1202																								
Day 1, Q3 months	Daily																								
900 mg	800 mg																								

	
minutes prior to the beginning of the ublituximab infusion. After Cycle 1, adjustments may be made to the antihistamine and/or corticosteroid dosing if deemed medically necessary. Please contact TG Therapeutics with any questions.
 
Ublituximab infusion in Cycle 1 only is split between Day 1 and Day 2, with the subject receiving up to 150 mg on Day 1 and remainder of the dose on Day 2 for subject crossing over from UTX-TGR-304 Arms B and D
 
For all subjects at risk for tumor lysis syndrome in the opinion of the treating investigator, prophylaxis with allopurinol or per recommended institutional standards should be considered.

Study Drugs	
Ublituximab is a glycoengineered, recombinant chimeric monoclonal antibody against the CD20 antigen, available as a 10 mg/mL or 25 mg/mL concentrate for solution for infusion, supplied by TG Therapeutics, Inc.
 
Umbralisib (TGR-1202) is a highly specific and orally available PI3K delta (<math>\delta</math>) inhibitor available in 200 mg tablets, supplied by TG Therapeutics, Inc.

Statistical Considerations	
Subjects from Treatment Arms B, C and D in Study 304 may enter this study upon documented progression of disease as confirmed by the independent central radiology review group. At the end of Study 304, non-progressed subjects from Treatment Arm A may also be enrolled to this Phase 2 Companion Study. It is undetermined the number of subjects that may enter this Companion Study, however it may not exceed the total number of subjects that have enrolled in Study 304.
 
As this study is intended as a compassionate use study for subjects progressing on Study 304, no formal hypothesis testing will be conducted. Efficacy and safety may be presented descriptively with subjects grouped by the treatment that the subjects received during the UTX-TGR-304 protocol prior to entering the Companion Study and overall.

Estimated Study Duration	
This study will remain open as long as there are subjects enrolling or who have been enrolled to Study UTX-TGR-304.

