### 4.1 OVERVIEW OF STUDY DESIGN

---

This Companion Study is intended for subjects who previously enrolled to the parent trial [UTX-TGR-304](#). Subjects from Treatment Arms B, C, and D with disease progression confirmed by the independent review committee (IRC), may be enrolled into this Companion Study. At the end of the UTX-TGR-304 study, non-progressed subjects from Treatment Arm A may also be enrolled to this Companion Study. Subjects from Treatment Arms B, C, and D may start treatment with ublituximab + TGR-1202, while subjects entering the Companion Study from Treatment Arm A may continue their treatment as specified by this protocol. All subjects enrolled to the Companion Study should receive ublituximab in combination with TGR-1202 (at the same dose and schedule as the Treatment Arm A in UTX-TGR-304) until they show disease progression, are unable to continue treatment for any reason such as lack of tolerability, or until the treatment is commercially available.

During the study period, all subjects will be evaluated for response by CT and/or MRI. Evaluations are to be obtained at approximately cycles 3, 6 and 12. Following cycle 12, evaluations should occur at least every 12 cycles unless clinically indicated more frequently. Subjects should remain on study treatment until the occurrence of definitive disease progression, unacceptable toxicity, or withdrawal from the study due to investigator decision or other reasons. Subjects who discontinue from study treatment (either for toxicity or physician choice) and have not progressed should continue to be followed for progression per institutional standard of care and reported in eCRF. Date of progression, beginning of new treatment, and/or death should be entered in the eCRF.

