 Unilateral bone marrow aspirate and/or biopsy performed at investigator discretion in subjects for whom assessment of extent of CLL involvement and bone marrow cellularity is important. In addition, a post-baseline bone marrow biopsy should be completed to confirm potential CR by radiological assessment.

 For women of child bearing potential, completed within 3 days of Cycle 1 Day 1.

 For women of child bearing potential, completed within 3 days of visit

 Must be obtained prior to ublituximab administration if on day of infusion.

 Must be done within 14 days of cycle 1 day 1

 For del(13q), del(11q), del(17p), and (12) trisomy, t(11:14)

 Scans should be completed approximately 45 days prior to Day 1 of Cycle 1. Radiology assessment should include CT or MRI imaging of chest, abdomen, and pelvis.

 Serum virology to include HBsAg, HbC antibody, HCV antibody and CMV IgG and IgM. If HbC antibody, HCV antibody or CMV IgM is positive, subjects must be evaluated for the presence of active HBV, HCV or CMV by PCR

 Q3 months CMV screening by PCR for all subjects.

 Peripheral blood sample may be analyzed by local lab. For subjects MRD negative by peripheral blood, a bone marrow should be completed to confirm MRD negativity. If a bone marrow is not completed, another peripheral blood sample should be collected to confirm the MRD negativity at least 12 weeks later. MRD should continue to be evaluated for subjects with PR/CR at response assessment intervals until 2 consecutive peripheral blood MRD negative results, or 1 negative peripheral blood MRD and 1 negative bone marrow MRD are observed.

 Subjects who received ublituximab on UNITY-CLL trial (Arm C), will not receive split dosing on Day 1 and 2 of cycle 1. Subjects should receive full dose on Cycle 1, Day 1 and will not receive Day 8, and 15 during Cycle 1.

 If clinically significant adverse event or abnormal result is observed that is not resolved by the end-of treatment visit, continue to monitor and record up through 30 days after study drug discontinuation.

TABLE 2: FOLLOW UP ASSESSMENTS SCHEDULE

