#### Treatment Schema for Subjects Crossing over from Arms B and D:

##### Cycle 1:

Ublituximab			TGR-1202
Day 1	Day 2	Day 8 & 15	Daily
150 mg	750 mg	900 mg	800 mg

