#### Treatment Schema for Subjects Crossing over from Arm C:

Cycle 1 should start 28 days after the last dose of ublituximab (given on the 304 study)

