##### Cycles 1 through 6:

Ublituximab	TGR-1202
Day 1	Daily
900 mg	800 mg

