### 6.2.1.1 INFUSION RELATED REACTIONS AND INFUSION RATE GUIDANCE - UBLITUXIMAB

---

Infusion related reactions including severe reactions have been reported with ublituximab administration in subjects with CLL. Guidelines are provided below for subjects who experience such reactions. Symptomatic infusion reactions, despite premedication, may be treated at the discretion of the treating physician, including but not limited to: oral acetaminophen 650 mg (or equivalent), corticosteroids, antihistamines, oxygen, and bronchodilators.

The following are recommended infusion rate reduction/delay guidelines for subjects who experience severe Infusion Related Reactions (IRR's) in which treatment should be interrupted. Final decision for infusion rate reduction/delay or discontinuation resides with the treating investigator.

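### The synopsis gives Arm C subjects two 900 mg ublituximab infusions in Cycle 1 (Days 8 and 15) that Section 6.1 and Table 1 footnote 15 withhold

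*Combined protocol and SAP*

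**What the plan says.** **Study Synopsis, Dosing Regimen.** The cycle tables are introduced with "This schedule is specific to subjects that were in UTX-TGR-304 Arms B, C, and D"; Arm A is set apart as continuing its existing schedule. One Cycle 1 table follows: ublituximab 150 mg on Day 1, 750 mg on Day 2, and 900 mg on each of Days 8 and 15. At the end of the row, a note on the split infusion assigns the "remainder of the dose on Day 2 for subject crossing over from UTX-TGR-304 Arms B and D". The row has no separate Arm C schedule.

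**Section 6.1.** The same Cycle 1 table stands under the heading "Treatment Schema for Subjects Crossing over from Arms B and D". Arm C has its own schema, with Cycle 1 starting 28 days after the last ublituximab dose on the parent study. Its first dose table is headed "Cycles 1 through 6" and lists 900 mg on Day 1.

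**Section 5, Table 1, footnote 15.** For subjects who had ublituximab on Arm C, split dosing is ruled out. The footnote goes on: "Subjects should receive full dose on Cycle 1, Day 1 and will not receive Day 8, and 15 during Cycle 1".

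**Section 4.1.** All subjects are to receive the combination "at the same dose and schedule as the Treatment Arm A in UTX-TGR-304". No exception is made for Arm C.

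**Section 6.2.1.2.** Flow rates are given for 150 mg and 750 mg on Cycle 1 Days 1 and 2, for 900 mg on Cycle 1 Days 8 and 15, and for 900 mg from Cycle 2 onward.

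**The concern.** For Arm C the synopsis and the body of the protocol cannot both be followed. The synopsis names Arm C and shows doses on Days 8 and 15 of Cycle 1; Section 6.1 and footnote 15 say there are none. The note on split dosing does not settle it, because it deals with Days 1 and 2 only.

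At stake are two unintended 900 mg infusions for any Arm C subject scheduled from the synopsis. Section 6.2.1.1 states: "Infusion related reactions including severe reactions have been reported with ublituximab administration in subjects with CLL".

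There is a smaller consequence for the analysis. Section 9.7 summarises dose and number of doses, and Section 9.3 removes major protocol deviations from the Per-Protocol population. Whether an Arm C dose on Day 8 is a deviation depends on which part of the protocol one reads.

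**Working it through.** The plan states no total to reproduce. The check sets the texts side by side and adds the listed doses.

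**Ublituximab for Arm C in Cycle 1**

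| Source | Day 1 | Day 2 | Day 8 | Day 15 | Total |
|---|---|---|---|---|---|
| Synopsis table as printed | 150 mg | 750 mg | 900 mg | 900 mg | 2,700 mg |
| Synopsis table with its note on the split | 900 mg | none | 900 mg | 900 mg | 2,700 mg |
| Section 6.1, Arm C schema | 900 mg | none | none | none | 900 mg |
| Table 1 footnote 15 | full dose (900 mg) | none | none | none | 900 mg |

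In the second row, the unsplit Day 1 dose is taken as 150 + 750 = 900 mg. The synopsis does not state it, but the total is the same either way.

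**Cycle 1**
- Difference: 2,700 − 900 = 1,800 mg, which is two 900 mg infusions.
- Ratio: 2,700 / 900 = 3.0.
- Infusion days: three (synopsis with its note) against one.
- Days 1 and 2 together come to 900 mg under every reading, so the whole difference comes from Days 8 and 15.

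**Cycles 1 to 6** (from Cycle 2 both sources give 900 mg on Day 1 of each cycle)
- Synopsis: 2,700 + 5 × 900 = 7,200 mg in 3 + 5 = 8 infusions.
- Section 6.1: 6 × 900 = 5,400 mg in 6 infusions.
- Ratio: 7,200 / 5,400 = 1.33.

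After Cycle 6 both sources give 900 mg every 3 months, so the difference stays at 1,800 mg.

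**Flow rate for the Arm C first dose** (Section 6.2.1.2)
- The Cycle 1 Day 1 and Day 2 rates cover 150 mg and 750 mg only.
- The 900 mg rates for Cycle 1 Days 8 and 15 run over 3 hours, starting at 50 mL/H.
- The 900 mg rates from Cycle 2 onward run over 90 minutes, starting at 200 mL/H.
- Arm C's unsplit 900 mg on Cycle 1 Day 1 falls under none of these labels. The two 900 mg candidates differ by 180 / 90 = 2 times in duration and 200 / 50 = 4 times in starting rate.

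**The case against.** The best reply is that the operative text is clear. Section 6.1 has a headed Arm C schema. Footnote 15 is attached to the ublituximab row of Table 1 and to its Day 2, Day 8 and Day 15 cells, which is where a site would look when booking those infusions. The amendment history records that Section 6.1 was revised to set out a schema for each parent arm, so the Arm C schedule was deliberate. The synopsis sentence can also be read as mainly separating subjects who start the combination from Arm A subjects who continue it. The split-dose note then signals that the table does not fit Arm C literally.

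On harm, the Day 8 and 15 doses are the protocol's own regimen for Arms B and D, and Arm C subjects have already had ublituximab. Nothing in the documents says that two more doses add risk for them. The study is descriptive, so no sample size or error rate is affected. The Section 4.1 wording and the missing flow rate are separate from the synopsis error.

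Most of this stands as an argument about weight. Intent is not in doubt, the risk that a site follows the synopsis is reduced, and the threefold figure applies to Cycle 1 only. None of it removes the contradiction: the synopsis still names Arm C above a table with Days 8 and 15, and the supplied text does not say that the body overrides the synopsis. The Section 4.1 and flow-rate points are secondary, and the main finding does not depend on them.

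**Conclusion.** The concern holds: the synopsis is wrong as written for Arm C and should be fixed. Followed literally, it adds 1,800 mg of ublituximab in two infusions, all in Cycle 1. That is three times the intended amount in that cycle and 1.33 times over Cycles 1 to 6.

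Taking the synopsis as the error assumes that Section 6.1 and footnote 15 carry the sponsor's intent; both are specific to the arm and they agree. The excess applies only to an Arm C subject dosed from the synopsis. The documents show no such case and do not establish added harm in previously exposed subjects. Confidence is high for the contradiction in the text and does not extend to any safety consequence.

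**What to change.** 1. In the synopsis, limit the Cycle 1 table to Arms B and D, and add the Arm C schedule from Section 6.1: 900 mg on Day 1 of Cycles 1 to 6, then every 3 months.
2. In Section 4.1, add an Arm C exception to the statement that every subject follows the Arm A dose and schedule.
3. In Section 6.2.1.2, state which flow rate applies to the unsplit 900 mg dose on Cycle 1 Day 1. Unlike the other changes, this needs a decision, because the existing text does not supply the answer.
4. Check once the Arm C Cycle 1 doses already recorded under Section 6.2.1.3 and summarised under Section 9.7, and settle before database lock whether any Day 8 or 15 dose counts as a major deviation.

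The cost is protocol wording and one look at existing dose records. No new data are needed.
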